Mild cognitive impairment is the most prevalent high risk state for the development of dementia. It is characterised by impairment in one or more cognitive domains, such as memory or attention, while performance of everyday activities is preserved. Four subtypes of MCI have been described. Amnestic MCI-single domain (AMCI) is characterised by isolated episodic memory impairment in the absence of other obvious cognitive or behavioural deficits and not related to pre-existing physical or emotional disorders. The current diagnostic criteria for AMCI include (1) memory complaint corroborated by an informant, (2) objective memory impairment for age (3) essentially preserved general cognitive function, (4) largely intact functional activities, and (5) not demented [Petersen 2004]. AMCI appears to represent a high-risk and prodromal state for AD with a 10 to 15% annual conversion rate to dementia compared to 1-2% in healthy elderly; longitudinal studies reveal a 80% dementia conversion rate after 6 years

[Petersen *et al.* 1999;Petersen *et al.* 2001;Fischer *et al.* 2007;Petersen 2004]. The other subtypes of MCI include amnestic MCI-multiple domains, non-amnestic MCI-single domain and non-amnestic MCI-multiple domains; each subtype respectively considered prodromal for AD or vascular dementia; dementia with Lewy bodies or frontotemporal dementia; dementia with Lewy body or vascular dementia [Petersen 2004]. Not all AMCI convert to AD but it appears to be a strong and prevalent risk indicator [Fischer, Jungwirth, Zehetmayer, Weissgram, Hoenigschnabl, Gelpi, Krampla, and Tragl 2007].

Physical exercise

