- To prospectively follow MCI patients to monitor the rate of conversion to dementia and to compare rate of conversion to historic controls.

Methods

Subjects

MCI Subjects

We plan to recruit 128 patients diagnosed with MCI (amnestic and non-amnestic) from the Derwent Memory Clinic at St Margaret's and Princess Alexandra Hospitals, Essex, UK. The general practitioner of all subjects will be informed of their participation in the study.

Inclusion criteria for patients with MCI

- Patients fulfilling criteria for AMCI [Petersen, Doody, Kurz, Mohs, Morris, Rabins, Ritchie, Rossor, Thal, and Winblad 2001]:
 - i. Memory impairment for age and education
 - ii. No impairment in other cognitive domains
 - iii. Normal social activities
 - iv. Patient is not demented
- 2. Patients diagnosed with other subtypes of MCI (cognitive impairment in one or more non-memory domain)
- Sedentary lifestyle with no regular participation in physical exercise defined as two or three times a week for at least 20 minutes duration, or participation in active organised sport more than once a week, in the previous six months.
- 4. Willing and able to give informed consent.
- 5. Availability and access to safe exercise environments, such as paths or roads with sidewalks for walking or cycling.
- At low risk from serious adverse effects from increased physical activity as indicated by performance on the revised Physical activity readiness questionnaire (PAR-Q).

Exclusion criteria for patients with MCI

- 1. Type 1 (insulin dependent) diabetes mellitus.
- 2. Blood pressure above 160/100 mmHg.
- 3. Body weight more than 140% of ideal body weight.
- 4. Musculoskeletal or other medical problems preventing safe participation in regular moderate intensity exercise (65-77% of predicted maximum heart rate). This will include a resting tachycardia (heart rate above 100 bpm) and history of myocardial infarction or unstable angina within the last month.

Participants with modifiable exclusion criteria will be reconsidered after successful management. Patients will be referred for medical /cardiological review and management prior to commencing exercise if indicated by the PAR-Q and the intervention will be guided by the PARmed-X.

Participants taking medications affecting heart rate will need to be on a stable dosing regime for 3 months prior to commencing in order to control for potential spurious results on fitness measures caused by these treatments.

Historic MCI control subjects

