Historic MCI control subjects will be identified from the Derwent Memory Clinic data base which contains data on more than 400 MCI patients. These controls will be used in the analyses for comparison of outcomes in treated and untreated patients. Controls will be matched on the following criteria:

- age
- gender
- MMSE score
- education

A placebo social contact control group will not be included as previous studies indicate no difference between social-contact and no-contact control groups on cognitive or functional measures [Willis, Tennstedt, Marsiske, Ball, Elias, Koepke, Morris, Rebok, Unverzagt, Stoddard, and Wright 2006;Willis *et al.* 1983;Clark *et al.* 1997].

Clinical assessment

The standard clinical workup includes a detailed history of cognitive impairment from the patient and an informant, a full psychiatric history, a mental state examination, a physical examination with an emphasis on neurological examination and a neuropsychological test battery. Measures/tests included are:

- National Adult Reading Test (NART) [Nelson 1991]
- The Mini-Mental state examination (MMSE) [Folstein et al. 1975]

- Cambridge Cognitive Examination (CAMCOG-R) [Huppert et al. 1995]
- Logical Memory Test [Wechsler 1997]
- Halstead Trail Making test (TMT) [Davies 1968]
- The Clinical Dementia Rating (CDR) [Berl 1988]
- Clifton assessment procedure for the elderly, Behavioural rating scale only (CAPE) [Pattie and Gilleard 1979]
- 15 item Geriatric Depression Scale (GDS-15) [Yesavage *et al.* 1982]

Trail design

We plan a longitudinal study where participants will serve as their own controls. Participants will start with **phase one** during which they will engage in 12 weeks DSD program designed to increase behavioural flexibility and therefore adherence with the planned physical, cognitive and social interventions in phase two. This will be followed by **phase two** during which they will take part in a 12 weeks physical, cognitive and social activity program. Outcome measures will therefore be collected at three time-points: baseline (Time 1), midway, week 12 (Time 2) and following phase 2 (Time 3).

Outcome measures

The main outcome is the development and implementation of the multimodal intervention program. Success will be measured as participant compliance during the program (% of participants compliant with intervention program), feedback on the interventions and continued engagement after completion.

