Secondary outcomes include measures of cardiovascular fitness, improvements on neurocognitive testing, everyday activities and quality of life.

Cardiovascular fitness, cognitive performance, activities of daily living and brain activation will be measured at baseline, after 12 weeks of phase 1 and at the end of phase 2.

1. Cardiovascular fitness measure

Cardiovascular fitness will be measured with a modified **Siconolfi Step Test** which has been validated in clinical samples [Marcora *et al.* 2007;Siconolfi *et al.* 1985]. The original test has a step height of 10 inches but we have found that this raises heart rate above 77% of predicted maximum heart rate, making it unsuitable for sub-maximal fitness testing. Our participants will step up and down a 6 inch (152mm) bench for three minutes, completing 17 (step up and down) cycles per minute. Heart rate (HR) will be measured during, immediately after completion of step -test and at one minute intervals for three minutes. The step-test will be paced using a metronome to ensure standard application. This sub-maximal stress test has a very low risk when combined with an exercise safety questionnaire such as the revised **Physical activity readiness questionnaire** (PAR-Q). Waist circumference and BMI (weight (kg) / height² (m)) will also be recorded.

2. Cognitive measures

Participants will complete the following cognitive measures:

- Visual and auditory divided attention task [Dannhauser *et al.* 2005]. This measures speed of processing and attentional set shifting.
- Verbal episodic encoding and recognition task [Dannhauser et al. 2008]
- Halstead Trail Making test (TMT) [Davies 1968]. This measures speed of processing (reaction time) and accuracy (corrected recognition).
- Verbal fluency [Lezack, 1995]
- Working memory tests: digit span forwards/ backwards [Miller, 1956]
- Verbal Reasoning and Working Memory [e.g. Hitch, 1976].

The standard neuropsychological test battery described above will be repeated annually as part of the standard clinical procedure in the memory clinic. This will provide long term follow-up data on all participants until they either make a full recovery or convert to dementia. 3. Measures of quality of life and everyday activities

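### Historic controls for the conversion comparison are matched on four factors only, without MCI subtype or the trial's eligibility criteria, so the contrast can be biased in an unknown direction

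*Protocol*

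**What the plan says.** All references are to the protocol.

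- *Study Aims*: the fourth aim is to follow MCI patients prospectively, "to monitor the rate of conversion to dementia and to compare rate of conversion to historic controls".
- *Historic MCI control subjects* gives the source of the controls: "Historic MCI control subjects will be identified from the Derwent Memory Clinic data base which contains data on more than 400 MCI patients". Their purpose is stated as "These controls will be used in the analyses for comparison of outcomes in treated and untreated patients". Then "Controls will be matched on the following criteria", followed by four items: age, gender, MMSE score and education. No index date, calendar period or eligibility condition is given for them.
- *MCI Subjects* and the inclusion and exclusion criteria: 128 patients, amnestic and non-amnestic. They must be sedentary, consenting and at low risk on the PAR-Q. Type 1 diabetes, blood pressure above 160/100 mmHg, weight above 140% of ideal, and conditions that prevent safe moderate exercise are exclusions.
- *Mild Cognitive Impairment* (introduction): amnestic MCI is described as high risk, with 10 to 15% converting per year. The other subtypes get no rate, but are distinguished by the dementia they precede: "each subtype respectively considered prodromal for AD or vascular dementia", and so on.
- *Cognitive measures*: the annual clinic battery is to give long-term "follow-up data on all participants until they either make a full recovery or convert to dementia".
- *Statistical analysis* and *Analysis*: paired comparisons, mean change with 95% CI, and repeated-measures ANOVA extended to background covariates. Conversion and the historic comparison are not mentioned.

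**The concern.** A matched historic comparison is only as good as the factors that make the groups alike. The matching list is fixed in the protocol and is short. It leaves out subtype, the one clinical feature that the introduction uses to separate kinds of MCI. It also leaves out the criteria that decide who may become a participant. Treated patients are volunteers who passed an exercise-safety screen and were still free of dementia at entry. As written, controls are any MCI patients in the database who fit on four variables.

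If such differences move the conversion rate, a contrast will appear whether or not the programme works. The programme is meant to delay dementia, and this is the only planned comparison of conversion. A spurious ratio in either direction could therefore influence the case for the later randomised trial.

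**Working it through.** **The plan's own figures.** The sample-size section concerns other comparisons, and its figures reproduce. For a within-subject change of 0.25 SD, n = ((1.96 + 0.842)/0.25)² ≈ 126, and the t-based power at n = 128 is 80.2%. The half-width of the 95% CI is t(0.975, 127)/√128 = 0.175 SD. No sample size, power or event count is given for conversion, so there is no plan figure to check on this point.

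**Inputs for the illustrations.** Only the amnestic rate p = 10 to 15% per year comes from the protocol. The subtype shares, the non-amnestic rate, the enrolment gap and the recovery figures are assumptions. There is no treatment effect in any illustration.

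**1. Subtype mix.** Annual risk = a·p + (1 − a)·q, with a the amnestic share and q the non-amnestic rate (5 or 10%, with q below p).

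| p | q | a, treated | a, controls | Risk, treated | Risk, controls | Ratio |
|---|---|---|---|---|---|---|
| 15% | 5% | 50% | 80% | 10.0% | 13.0% | 0.77 |
| 15% | 5% | 50% | 70% | 10.0% | 12.0% | 0.83 |
| 10% | 5% | 50% | 70% | 7.5% | 8.5% | 0.88 |
| 15% | 10% | 50% | 70% | 12.5% | 13.5% | 0.93 |
| 15% | 10% | 70% | 50% | 13.5% | 12.5% | 1.08 |
| 10% | 5% | 70% | 50% | 8.5% | 7.5% | 1.13 |
| 15% | 5% | 70% | 50% | 12.0% | 10.0% | 1.20 |

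The ratio lies on either side of 1 depending on which group has more amnestic patients, and the protocol gives neither share.

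**2. Eligibility.** Side by side, the criteria pull in different directions. Low risk on the PAR-Q, the blood-pressure and weight limits, fitness for exercise and willingness to consent plausibly select healthier participants. The sedentary requirement may act the other way, because the *Physical exercise* section of the introduction links regular exercise to lower dementia risk. No net direction follows.

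**3. Start of follow-up.** Suppose both groups are counted from diagnosis, and participants enrol L years later and must still be dementia-free. At a constant hazard the 3-year ratio is [1 − (1 − p)^(3−L)] / [1 − (1 − p)³].

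- p = 10%, L = 0.5: 0.232/0.271 = 0.85. L = 1: 0.190/0.271 = 0.70.
- p = 15%, L = 0.5: 0.334/0.386 = 0.865 (0.87 to two places). L = 1: 0.278/0.386 = 0.72.

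This bias favours treatment, but only under that counting. If participants were counted from enrolment, the constant-hazard ratio would be 1.

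**4. Recovery.** Take 35% of patients at 4% per year and 65% at 16% per year. The true 5-year risk is 0.35(1 − 0.96⁵) + 0.65(1 − 0.84⁵) = 44.3% in both groups. Let 30% (one group) or 60% (the other) of the low-risk patients still unconverted at year 1 recover then.

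- Censoring at recovery: with 30%, 1 − 0.882 × (0.2352 × 0.96⁴ + 0.546 × 0.84⁴)/0.7812 = 46.8%. With 60%, the low-risk term becomes 0.1344 and the divisor 0.6804, giving 50.0%.
- Recovery as a competing event: with 30%, 0.118 + 0.2352(1 − 0.96⁴) + 0.546(1 − 0.84⁴) = 42.8%. With 60%, 41.2%.

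Neither method restores equality when recovery differs between groups. Censoring raises the figure for the group that recovers more, and the competing-event treatment lowers it. Counting conversions after recovery returns 44.3% in both.

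**The case against.** The strongest reply is that this is a feasibility study. Its main outcome is developing and implementing the programme, its principal analysis is within-subject change, and conversion is not listed among the main or secondary outcomes. That stands, and it limits the reach of the point.

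A reader might infer that the omissions make the programme look better. The protocol does not support that. It gives a conversion rate for amnestic MCI only and compares it with healthy elderly people, not with other subtypes. The subtype mix is unknown, and the sedentary criterion may work against the treated group.

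A reader might also take the start date or the recovery wording as stated errors. The missing index date is an omission that an analysis plan could fill, so its effect is conditional. The recovery sentence describes clinic follow-up and states no censoring rule. If both groups are handled alike, the contrast is distorted only when recovery differs between them. Nor does the protocol say that people who declined or failed screening will serve as controls.

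Finally, the broad word for outcomes in the controls section might be read as planning a historic comparison of the fitness, attention and quality-of-life measures. For those, participants are their own controls, so this is at most loose wording.

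None of this answers the fixed four-factor matching list or the lack of any stated adjustment.

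**Conclusion.** The point holds in a limited form. As written, the conversion contrast is open to confounding by MCI subtype and by eligibility, and no stated adjustment compensates. With no treatment effect, the subtype mix alone could give an apparent ratio of about 0.77 to 1.20 under the assumed shares and non-amnestic rates. A counting mismatch of half a year to one year could give about 0.87 down to 0.70, if both groups are counted from diagnosis. These are illustrations and not estimates of the actual bias, because only the 10 to 15% amnestic rate comes from the protocol. The supportable statement is that the contrast can be biased in a direction not known.

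It would go too far to say that the fourth aim cannot be met, because its first half, monitoring conversion, needs no controls.

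**What to change.** In *Historic MCI control subjects*:

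1. Add MCI subtype to the matching factors.
2. Restrict controls to those who meet every trial eligibility criterion that can be checked in the clinic record, including activity level where it is recorded.
3. Start each control's follow-up at a clinic review where the person still has MCI, at the same time since diagnosis as the matched participant had at Time 1. Count participants from Time 1.
4. In both groups, count conversions the clinic records after a recovery, where available, and do not censor at recovery.
5. Report the conversion contrast as exploratory. Willingness to take part and the PAR-Q result are not among the listed clinic measures, so some difference between the groups will remain.

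The cost is database work, a smaller control pool and wider intervals. With more than 400 records for 128 participants (400/128 ≈ 3.1 each before restriction) there is some room to be selective. No new patients or study procedures are needed.

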Socialising exercises a number of cognitive skills including memory (facial recognition, naming, episodic encoding and recall), attention (divided attention for simultaneous monitoring of non-verbal and verbal communication) and executive control of these functions. Supervised socialising in groups provides opportunity to involve participants in cognitively stimulating activities that also promote emotional well-being. Groups based strength and coordination training improves physical parameters but also improves quality of life and provides cognitive stimulation (McLaughlin 1995; Hickey 1992). Health promoting information, such as the benefits of exercise and dietary advice, can be provided in group settings. The social cohesion that develops in groups increases compliance and provides support for participants. Group settings can also be used to introduce activities that diversify the everyday activities of participants and thereby provide cognitive stimulation.

Mutimodal intervention programs

Multimodal intervention programmes which include physical exercise, cognitive training and socialising are thought to be the most likely to delay the need for care in those at risk (Oswald et al. 2007). Studies have reported improvement in physical status, functional abilities, mood and engagement in physical activity following multimodal multi-sensory interventions (Heyn 2003; Oswald et al. 2007). A combination of physical and cognitive exercise appears most beneficial, leading to improved independence and mood.

Implementing and monitoring interventions with information technology

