Quality of life will be measured on the World Health Organization Quality of Life (WHOQOL) – BREF and change in every day activities on the Alzheimers' Disease Cooperative Study MCI Activities of Daily Living Scale (ADCS-MCI-ADL)[Galasko *et al.* 1997].

4. Measure of brain activation /perfusion with near infrared spectroscopy heamoenephalography (NIRS-HEG)

We will collect brain activation data from all participants at the three time points during administration of the divided attention paradigm which runs for 5 minutes.

We will use a CE marked Oxymon Mk (Artinis, Netherlans) to measure changes in light attenuation at four discrete wavelengths (775,825,,850 and 905 nm) using four laser diodes as light sources and photon multiplier tube as detector. Sensors will be placed over the left prefrontal (F3), the superior parietal (P3) and the occipital cortex (O1) and the right frontal pole (Fp2), according to the international 10-10 system developed for EEG. This portable system does not involve any ionising radiation.

Treatment sessions

1. Physical exercise

Participants will be asked to complete 36 training sessions at a frequency of two to three per week. Half of all the groups (Feedback participants, **FP-group**) will be randomly allocated sound and vibration feedback to help them to stay in a predetermined training zone. Heart rate for the moderate training zone (less than 60% of VO2 max; 65-77% of maximum heart rate) will be determined for each participant from their predicted maximum heart rate (HR max = 220 – age). The other groups will not receive feedback but heart rate will still be measured (Monitoring participants, **MP-group**); this group will receive instruction on utilising subjective reports of effort to guide their optimal level of effort. Assignment to FP-group and MP-group will alternate so equal numbers are obtained for statistical comparison. In addition each participant will be issued

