with a large poster providing visual instructions of how to use the equipment and do a 10 minute warm-up routine (Appendix B). They will receive home visits and supervision at sessions 1, 3, 8, 14 and 20 (see Appendix C for a timelines). They will also receive regular weekly telephone contact to provide support and monitor progress. Heart rate monitors (Oregon Scientific SE102I) measure electrocardiographic signals via a chest strap. Heart rate zones are programmed into the monitors and auditory signals and vibration of the monitor attached to the arm provides feedback and alerts the patient when heart rate is outside the preset parameters. Heart rate monitors will be programmed by the research team. An electronic data logger (Oregon Scientific WM100) which collects continuous data from the chest strap will be activated during activity so that heart rate data during physical activity is captured for later analysis.

Patients taking beta blocker medication will exercise at a heart rate equivalent to a specific effort (14 on the Borg scale) as these medications lower heart rate and result in sub optimum training when training zones are calculated as described above [Tabet *et al.* 2008;Borg 1970]. The relevant rate will be determined during the initial supervised walking sessions.

2. Cognitive training

In addition to Physical exercise participants will be asked to complete 12 cognitive training sessions at a frequency of 1-2 per week. Training will take place on an individual and group basis, both supervised and unsupervised. The duration of training sessions will vary from 30 to 90 minutes depending on the type of training. A variety of training techniques will be employed with the aim to improve specific cognitive components such as attention, speed of processing, working memory, problem solving and reasoning. For training we will use the program developed by Lumosity (www.lumosity.com). Centre-group participants will have access to online resources either at training centres provided and staffed by the Adult Community Learning (ACL) Service in Essex, or at home. Online-group participants will be provided with access to computers and the internet for the duration of the study. These participants will not require any existing computing skills as all content will be accessed and supervised remotely by the researchers and ACL staff. Participation on the cognitive Lumosity program will be anonymised and data will be collected on the time and duration

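### Heart-rate feedback is allocated by whole group although it is a setting on each participant's own monitor, and no group term is planned, so the FP v MP comparison is less precise than it will appear

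*Protocol*

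**What the plan says.** Under Treatment sessions, 1. Physical exercise, the protocol allocates sound and vibration feedback to "Half of all the groups (Feedback participants" (the FP-group). For the rest, "The other groups will not receive feedback but heart rate will still be measured" (the MP-group), and these participants are taught to judge their effort subjectively. The comparison is intended: "Assignment to FP-group and MP-group will alternate so equal numbers are obtained for statistical comparison".

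The same section describes the feedback as individual:
- The training zone "will be determined for each participant from their predicted maximum heart rate".
- Delivery is personal: "auditory signals and vibration of the monitor attached to the arm provides feedback and alerts the patient".
- "Heart rate monitors will be programmed by the research team".
- Training is supported person by person: "They will receive home visits and supervision at sessions 1, 3, 8, 14 and 20", with weekly telephone calls.

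Groups of 8 appear under 3. Socialising, for centre participants, who meet weekly with tutors for 12 weeks. No size is given for online groups. The Introduction (Social exercise) says: "The social cohesion that develops in groups increases compliance and provides support for participants".

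The Statistical analysis and Analysis sections name paired t tests, ANOVA and repeated-measures ANOVA, extended to background covariates such as age and sex. Group is not mentioned. Sample Size gives no figure for FP v MP.

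**The concern.** When whole groups are allocated, members of a group share an arm and also a tutor, a meeting schedule and whatever cohesion develops. The protocol itself says that cohesion affects compliance, and compliance is one of its measures of success. If groups were allocated at random, these influences would add variance rather than systematic bias, but that variance is shared within groups and does not shrink as members are added.

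Two things follow. An analysis that treats participants as independent understates the standard error of the FP v MP difference. An analysis that respects the groups has about 16 units instead of 128 and loses power. Nothing in the protocol ties a monitor setting to a social group, so the loss looks avoidable. The point concerns the unit of allocation, and it would remain if groups were drawn from a perfect random list.

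**Working it through.** **Inputs from the protocol.** N = 128; groups of 8 (centre participants only); FP and MP equal, so 64 v 64; 5% significance. A difference of 0.5 SD is borrowed from the protocol's only two-group power statement.

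**Assumptions.** All 128 participants are in groups of 8, giving 16 groups, 8 per arm. ICC is 0.01, 0.05 or 0.10. Tests are two-sided.

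**Step 1: the protocol's own two-group figure.** For community v centre it states 0.5 SD with 80% power at n = 64. With independent participants, SE = √(2/64) = 0.1768 and 0.5/0.1768 = 2.828. Power is Φ(2.828 − 1.96) = 80.7%, or 80.1% by noncentral t. The figure reproduces. It is not a claim about FP v MP.

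**Step 2: group allocation, groups ignored in the analysis.** The design effect is DE = 1 + (8 − 1) × ICC. The true error of a nominal 5% test is 2 × [1 − Φ(1.96/√DE)].

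| ICC | DE | 1.96/√DE | True error |
|---|---|---|---|
| 0.01 | 1.07 | 1.895 | 5.8% |
| 0.05 | 1.35 | 1.687 | 9.2% |
| 0.10 | 1.70 | 1.503 | 13.3% |

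**Step 3: power for 0.5 SD with a correct analysis (noncentral t).**
- Group allocation, group-level test: SE = √(2 × DE/64), 16 − 2 = 14 df.
- Individual allocation within groups, group in the model: SE = √(2 × (1 − ICC)/64), 128 − 16 − 1 = 111 df.

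| ICC | SE, by group | Power | SE, within group | Power |
|---|---|---|---|---|
| 0.01 | 0.183 | 72.0% | 0.176 | 80.5% |
| 0.05 | 0.205 | 62.0% | 0.172 | 82.0% |
| 0.10 | 0.230 | 52.4% | 0.168 | 84.0% |

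**Step 4: only centre participants clustered.** Suppose 64 are in 8 groups and 64 online participants are independent.
- Power: combine the two halves by inverse variance, 1/SE² = 32/(2 × DE) + 32/2, with (8 − 2) + (64 − 2) = 68 df. The SE is 0.180, 0.190 and 0.198, and power under group allocation is 78.3%, 73.9% and 70.0%.
- Error if groups are ignored: average variance inflation is (DE + 1)/2 = 1.035, 1.175 and 1.35, giving about 5.4%, 7.1% and 9.2%.

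**Step 5: how much contamination would cancel the gain?** I found the diluted difference at which within-group allocation has only the power of group allocation in Step 3. The 0.5 SD would have to shrink by about 10% at ICC 0.01, 21% at 0.05 and 32% at 0.10.

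**The case against.** **Contamination.** This is the strongest argument. MP participants are taught to pace themselves by perceived effort, and such advice can be passed on, unlike an alert from someone else's monitor. Centre groups meet weekly and discuss the previous week's tasks, so a mixed group could dilute the contrast. This stands as a real trade-off: by Step 5, a dilution of about 10% would remove the power advantage if the ICC is near 0.01. The protocol does not give this as its reason, and even if it did, the analysis would have to respect the groups.

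**Start date and season.** A reader might infer that these are confounded with feedback. If allocation alternates as groups start, FP and MP groups are interleaved in time and both are roughly balanced. Tutor and cohesion remain.

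**Number of units.** A reader might infer that the comparison rests on 8 units if only centre participants form groups. That would discard 64 online participants, whom the text does not exclude. Step 4 keeps them, and the loss is smaller.

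**Size of the ICC.** Exercise is largely individual, judging by the personal monitors, home visits and calls, so the ICC for fitness or intensity may be low. That is fair, and it is why a range is shown.

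**Wording.** Group in FP-group could be only an arm label. However, the text divides the groups, in the plural, into half and the others, which makes groups the units allocated.

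**Analysis detail.** A group term could be set in a statistical analysis plan that is not shown. That could correct the error rate but would not recover the power, because the unit of allocation is fixed in the protocol.

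**Conclusion.** The point holds as a weakness in a subsidiary comparison. Feedback is allocated by group without a stated reason, and the analysis as written does not account for it. Under 16 groups of 8 and ICC 0.01 to 0.10, the consequence is either a true error of about 5.8% to 13.3% or, analysed correctly, 72% to 52% power for 0.5 SD where individual allocation would give 80.5% to 84%. With online participants independent, power is about 78% to 70%. The ICC and the size of any online groups are assumptions. Near ICC 0.01 the loss is modest.

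A reader might infer that the protocol's 80% power statement is wrong. It is not: it concerns community v centre, it reproduces, and no power is stated for FP v MP. Nor does the point touch the main outcome (implementation and compliance of the programme) or the principal analysis of within-participant change, since neither depends on FP v MP.

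**What to change.** Preferred: amend Treatment sessions, 1. Physical exercise so that feedback is allocated to individuals, 4 FP and 4 MP within each group of 8, from a concealed random list. Allocate online participants in random blocks by start date. State that the FP v MP analysis includes group as a factor.

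The cost is an amendment and one allocation list; monitors, visits and sample size are unchanged. The downside is that members will notice that monitors differ, and MP effort instruction may be shared at weekly sessions, diluting the contrast somewhat.

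If group allocation is kept to avoid this, state that reason and analyse FP v MP with group as a random effect or on group means. Report the estimate with its interval and the observed ICC, which would also help in planning the future randomised trial.
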